## **4 Definitions**

### **4.1 Baseline**

Study Day 0 is defined as the vaccination date. The values used for baseline summaries will be the last evaluation on or before the vaccination date.

### **4.2 Analysis Populations**

Any mother participants found to be ineligible and who the study team determine should not be included in any analyses, will be included in accrual and eligibility summaries only. Protocol deviations will be summarized but should not result in any participants being excluded from analyses.

Safety population: Safety analyses will be as-treated and include all women who received study vaccination and all infants who were born alive.

Immunogenicity population: The primary immunogenicity analyses will use an as-treated approach, limited to women who received study vaccination and all infants who were born alive. In addition, the primary immunogenicity analysis in infants will be restricted to those who did not receive the PCV-10 vaccination prior to the week 8 evaluation. If more than one child is born to a pregnant woman, one child will be randomly selected to be included in the primary immunogenicity analyses.

For the immunogenicity analysis in secondary objective #6, infants who did not receive the PCV-10 vaccinations within the correct windows will be excluded. The windows are described below in section 5.1.

## 5 Statistical Methods

Baseline characteristics will be summarized by treatment group but with no statistical comparisons comparing arms.

Statistical tests will not be adjusted for interim monitoring or multiple comparisons. The Chi-square tests will be used to compare rates of response following vaccination between the vaccinated groups and placebo group. The statistical tests will be two-sided with a nominal significance level of 0.05. Categorical data will be summarized using N (%) and 90% or 95% confidence intervals (CIs), and continuous data using N, min, Q1, median, Q3, max, and mean (STD) (when appropriate) and 95% CI.

Any modifications to outcome measures after the team has seen data collected after entry will be identified as *post hoc* in the analysis report.

### 5.1 Visit and Evaluation Schedule

#### Maternal Schedule:

Study visits for women were conducted on Day 0 (day of vaccination), week 1 (with a window of +3 days), week 4 and at labor and delivery (L&D) (each with a window of +7 days), and at 24 weeks post-delivery (with a window of  $\pm 28$  days) or as needed for unscheduled visits.

At week 24 post-delivery, the women had the possibility of registering to Step 2 or Step 3.

#### Infant Schedule:

Study visits for infants were conducted at birth (with a window of +7 days), week 8, which should be  $\leq 7$  days before the 1st dose of PCV-10 (with a window of +14 days), week 16, which should be  $\leq 7$  days before the 2nd dose of PCV-10 (with a window of  $\pm 28$  days), week 24, which

should be  $\geq$  28 days after the 2nd dose of PCV-10 (with a window of 28 days), or for Invasive Pneumococcal Disease (IPD).

## 5.2 Safety Primary Objectives

Only mothers who received vaccination and infants who were born alive will be included in the safety analyses.

The number and proportion of women and children experiencing at least one primary safety outcome measure will be summarized by treatment group with 90% CIs. The types of primary safety outcome measures that occur will be summarized.

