## 3 Protocol Overview

### 3.1 Study Design

**DESIGN:** A double-blind, randomized, placebo-controlled study to evaluate the safety and immunogenicity of two pneumococcal vaccines in HIV-infected pregnant women in their second or third trimester on highly active antiretroviral therapy (HAART) and their infants.

**SAMPLE SIZE:** Approximately 345 Human Immunodeficiency Virus (HIV)-infected pregnant women and their 345 infants (690 participants), equally distributed among three treatment arms to obtain  $\geq 100$  evaluable pairs/arm (300 total pairs, or 600 total participants).

**REGIMEN:** **Step 1.** Pregnant women will be randomized between  $\geq 14$  weeks (14 weeks 0 days) to  $< 33$  weeks (32 weeks 6 days) of gestation to one of three blinded treatment arms (administered on Day 0):

- Arm 1A: pneumococcal polysaccharide 23-valent vaccine (PPV-23);
- Arm 1B: pneumococcal conjugate 10-valent vaccine (PCV-10); or
- Arm 1C: placebo.

**Step 2.** Women randomized to Arm 1C (placebo) who complete Step 1 will be screened for entry into Step 2 and will be randomized to receive PPV-23 (Arm 2A) or PCV-10 (Arm 2B) at 24 weeks after delivery. The women who received active vaccine during pregnancy (Arms 1A and 1B) will stop study at 24 weeks after delivery.

**Step 3.** Women who were initially randomized to Arm 1C and meet an exclusion criterion for Step 2 due to new pregnancy will be enrolled in Step 3 and receive open label PCV-10 at the last study visit (which coincides with Step 1 24 weeks post-delivery).

All infants will receive PCV-10 per local standard of care.

STUDY DURATION: Up to 60 weeks for women (approximately 28 weeks pre-delivery; 32 weeks post-delivery) and up to 28 weeks for infants.

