### 3.2 Study Objectives and Outcome Measures

#### Primary objectives and outcome measures:

1. To assess the safety of the PCV-10 and PPV-23 vaccines in HIV-infected pregnant women on HAART.

- Outcome measures:

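### Section 5.2 prespecifies no vaccine-minus-placebo safety estimate, so any excess risk is left to informal comparison of per-arm 90% CIs

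*SAP*

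**What the plan says.** SAP section 3.1 describes "A double-blind, randomized, placebo-controlled study to evaluate the safety and immunogenicity of two pneumococcal vaccines" in HIV-infected pregnant women and their infants. One of the three equal blinded arms is "Arm 1C: placebo". The first primary objective in section 3.2 is "To assess the safety of the PCV-10 and PPV-23 vaccines in HIV-infected pregnant women on HAART".

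For that objective, section 5.2 plans the number and proportion of women and children with at least one primary safety outcome, which "will be summarized by treatment group with 90% CIs", and a summary of the types of outcome. It plans nothing further.

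The only general vaccine-versus-placebo comparison is in section 5, where chi-square tests are to "compare rates of response following vaccination between the vaccinated groups and placebo group". In context that means immune response. The tests in section 5.3 compare PCV-10 with PPV-23, and the secondary objectives that name placebo concern antibodies.

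Section 4.2 defines the safety population: "Safety analyses will be as-treated and include all women who received study vaccination and all infants who were born alive". That placebo recipients belong to it has to be inferred from the phrase *by treatment group* in section 5.2.

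**The concern.** Several primary safety outcomes in section 3.2 have no causality filter. For mothers these are Grade 3 or higher events up to week 4 and Grade 4 events or death after week 4. For infants they are Grade 3 or higher events, congenital defects, HIV infections, and pneumonia or invasive pneumococcal disease. Such events can occur without vaccination, so one arm's proportion mixes background with any vaccine effect. The concurrent randomised placebo arm is what separates the two, and section 5.2 specifies no estimate that uses it directly.

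A reader of the planned table has three separate intervals to set side by side. Taking overlap as a sign of no difference is stricter than an ordinary 5% comparison, and in a safety analysis that strictness works towards missing harm. If the contrast is computed later, its outcome, method and confidence level will be chosen after the data are known.

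**Working it through.** **Inputs from the SAP.** About 345 women and their 345 infants in three equal arms (section 3.1): 345/3 = 115 pairs per arm, with at least 100 evaluable. Tests are two-sided at 0.05 without multiplicity adjustment (section 5). Per-arm intervals are 90% (section 5.2). The SAP gives no safety event rate, margin or power, so there is no figure of its own to reproduce. All event counts and rates below are assumptions.

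**1. What non-overlap of two 90% CIs demands.** With equal standard errors *s*, two intervals of half-width 1.645*s* separate only when the difference exceeds 2 × 1.645*s*. The standard error of the difference is √2 × *s*. Non-overlap therefore needs |z| > 2 × 1.645/√2 = 2.33, a two-sided level of about 0.020. The SAP's own tests use 0.05.

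**2. Example at 115 per arm: placebo 12, vaccine 24.**
- Exact (Clopper-Pearson) 90% limits are the 0.05 quantile of Beta(x, n−x+1) and the 0.95 quantile of Beta(x+1, n−x).
- 12/115 = 10.4%, limits 6.1 to 16.4%. 24/115 = 20.9%, limits 14.8 to 28.1%. They overlap between 14.8 and 16.4%.
- Difference: 20.87 − 10.43 = 10.4 points.
- Newcombe 95% CI, from Wilson 95% limits of 6.07 to 17.36% (12/115) and 14.44 to 29.18% (24/115):
  - lower = 10.43 − √[(20.87−14.44)² + (17.36−10.43)²] = 10.43 − 9.44 = 1.0
  - upper = 10.43 + √[(29.18−20.87)² + (10.43−6.07)²] = 10.43 + 9.38 = 19.8
- Uncorrected chi-square: pooled rate 36/230 = 0.1565; 0.1043²/(0.1565 × 0.8435 × 2/115) = 4.74, p = 0.029.

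**3. Example at 100 per arm: placebo 5, vaccine 14.** The exact 90% CIs are 2.0 to 10.2% and 8.7 to 21.0%, which overlap. The difference is 9.0 points, Newcombe 95% CI 0.7 to 17.6.

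**4. Where the planned table would show an excess.** At 100 per arm the smallest vaccine-arm counts are:

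| Placebo events | 95% CI for the difference excludes 0 from | Exact 90% CIs separate from |
|---|---|---|
| 5 | 14 | 16 |
| 10 | 20 | 24 |
| 20 | 33 | 36 |
| 30 | 44 | 47 |

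The loss of sensitivity is two to four events per comparison.

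**5. Precision of the added estimate.** At an assumed 20% in both arms with n = 115, the simple half-width is 1.96 × √(2 × 0.2 × 0.8/115) = 10.3 points. Newcombe half-widths when the observed rates are equal:

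| n per arm | Assumed rate | 90% CI | 95% CI |
|---|---|---|---|
| 100 | 5% | ±5.5 | ±6.8 |
| 100 | 10% | ±7.2 | ±8.7 |
| 100 | 20% | ±9.3 | ±11.1 |
| 100 | 30% | ±10.6 | ±12.6 |
| 115 | 20% | ±8.7 | ±10.4 |

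**The case against.** The strongest defence is that the analysis matches its objective. The SAP writes *compare* where it wants a contrast, and the primary objectives worded that way get a chi-square test. The safety objective is worded *assess* and gets description. This stands: nothing in the plan is contradicted.

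A reader might infer that the planned output cannot show whether either vaccine adds risk. The SAP does not support that. Counts and proportions by arm are to be reported, so a difference can be derived from them, and a large excess would separate the intervals. Nor does the SAP say that arms will be judged by overlap of intervals. That is a risk in how the table is read and not a planned method.

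Other points have partial force:
- One maternal outcome is limited to events judged related to treatment, in a double-blind trial, and event types are summarised. This helps with attribution, but it rests on individual causality judgement, does not cover infants, and does not replace a randomised contrast.
- Table outlines are deferred to the Analysis Implementation Plan, which is not at hand and may contain a difference column. The statistical approach, however, is set in the SAP, and section 5.2 sets a per-arm summary.
- The 12 versus 24 example lies near a boundary: p is 0.046 with continuity correction and 0.045 by Fisher's exact test. It illustrates a general property of separate intervals and is not a forecast for this trial.
- A wide difference interval that includes zero can also be misread as no difference. It does at least display the imprecision.

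**Conclusion.** The point holds as a worthwhile and nearly free improvement, not as an error in the plan. Section 5.2 specifies no vaccine-versus-placebo safety estimate, although a concurrent randomised control exists and safety is a primary objective. Informal comparison of the per-arm 90% CIs corresponds to a two-sided level of about 0.02 when standard errors are equal. At 100 per arm it needs two to four more vaccine-arm events than a 95% CI for the difference before an excess stands out. A moderate excess could be overlooked; a large one would not be. These sizes rest on assumed placebo rates of 5 to 30% and on exact per-arm intervals, because the SAP states neither rates nor an interval method. The added estimate would itself be imprecise, at about ±10 points for a 20% rate.

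**What to change.** Keep the per-arm table. Add to section 5.2 the risk difference for PCV-10 minus placebo and for PPV-23 minus placebo, with a two-sided Newcombe or Miettinen-Nurminen CI, labelled as estimation with no hypothesis test. State the confidence level and the reason for it: 95% matches the 0.05 level in section 5, and 90% matches the per-arm intervals. Give the differences separately for:

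- **Women with at least one Step 1 primary safety outcome**, counting only events before any Step 2 or Step 3 vaccination. The outcomes in section 3.2 span Steps 1 and 2, and Arm 1C women can receive active vaccine in those later steps, so without this rule the control group would not stay unvaccinated.
- **Infants with at least one primary safety outcome**, counting one unit per mother or using a cluster-robust interval if twins are included. Selection of one child per mother in section 4.2 applies only to immunogenicity, and the standard intervals assume independent infants.

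State in section 4.2 that placebo recipients are in the safety population.

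The cost is one table from data already collected, with no extra participants. The downside is four more unadjusted intervals (two contrasts, two populations) that need cautious reading.

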## 5.3 Immunogenicity Primary Objectives

### Maternal:

This is an as-treated analysis including only the women who have been vaccinated.

Summaries will include: (i) the proportion (%) and 95% CI of women vaccinated with PCV-10 or with PPV-23 vaccines who had a  $\geq$ two-fold increase to  $\geq 1$  serotype in ELISA-measured IgG PNC antibody concentrations from baseline to 28 days after immunization in Step 1 (as measured at study week 4). The difference in proportions between the vaccinated groups will be assessed using a Chi-Square test; (ii) the proportion (%) and 95% CI of women vaccinated with PCV-10 or with PPV-23 vaccines who had ELISA-measured IgG PNC antibody levels  $\geq 0.35\mu\text{g/mL}$  at week 4 after immunization in Step 1 to  $\geq 1$  of the serotypes listed above.

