## 1 Introduction

This Primary Statistical Analysis Plan (SAP) outlines the general statistical approaches that will be used in the primary statistical analysis of NICHD P1091. The focus is on analyses that address the study's primary and secondary objectives, as well as summaries of the primary and secondary outcome measures that will be posted on ClinicalTrials.gov. It will facilitate discussion of the statistical analysis components among members of the study team and provide agreement between the team and statistician regarding the analyses to be performed and presented in the primary statistical analysis report. Detailed outlines of tables and coding descriptions that will be included in the primary statistical analysis report are included in the Analysis Implementation Plan (AIP).

Analyses for the primary statistical report will be initiated once the last participant has completed the last study visit, all laboratory data are available, all queries have been resolved, and the database has been frozen for analysis. This report will be used for submission of results to ClinicalTrials.gov. Results are required to be submitted within one year of the primary completion date (PCD), which is the date the last participant is examined for the purposes of data collection for the primary outcome measure. For this study, the PCD is based on the last study visit.

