#### Neonatal:

- Grade  $\geq 3$  AEs
- Congenital defects

- HIV infections
- Pneumonia or IPD

2. To compare the immunogenicity of PCV-10 with PPV-23 vaccines in HIV-infected pregnant women on HAART.
  - Outcome measure:
    - Raw values and fold change in ELISA-measured IgG PNC antibody concentrations from baseline to week 4 in Step 1 to  $\geq 1$  serotype. Serotypes measured by ELISA are: 1, 4, 5, 6B, 7F, 14, 23F and 33F.
3. To compare the level of Pneumococcal (PNC) antibodies at 8 weeks of life in infants born to mothers who received PCV-10 or PPV-23 vaccines.
  - Outcome measures:
    - ELISA-measured IgG PNC antibody levels  $\geq 0.35\text{ug/mL}$  at 8 weeks of age for  $\geq 1$  serotype from those listed above.

Secondary objectives and outcome measures:

1. To compare the level of transplacentally transferred vaccine-serotype PNC antibodies in infants born to mothers who received PCV-10 or PPV-23 versus placebo.
  - Outcome measure: Average ratio of infant/mother ELISA-measured IgG PNC antibody levels across the serotypes listed above, measured at birth/delivery
2. To compare the immunogenicity of PCV-10 and PPV-23 vaccines with placebo in HIV-infected pregnant women on HAART.
  - Outcome measure: ELISA-measured IgG PNC antibody concentrations at week 4 in Step 1, in all treatment groups
3. To compare the persistence of vaccine-serotype PNC anti-capsular antibodies for up to 24 weeks after delivery in HIV-infected women vaccinated with PCV-10, PPV-23 or placebo.
  - Outcome measure: ELISA-measured IgG PNC antibody concentrations at labor&delivery and week 24 post-delivery in Step 1, in all treatment groups
4. To compare maternal antibody responses to PPV-23 or PCV-10 administered during pregnancy with responses to PPV-23 or PCV-10 administered 24 weeks postpartum.
  - Outcome measure: ELISA-measured IgG PNC antibody concentrations at week 4 in

Step 1 and at week 4 in Step 2, in the women who received PPV-23 or PCV-10

5. To evaluate the effect of the following factors on the magnitude and persistence of the maternal antibody responses to PCV-10 and PPV-23: maternal age, ethnicity, cluster of differentiation 4 (CD4), cluster of differentiation 8 (CD8), plasma HIV RNA and gestational age at immunization.
  - Outcome measure: ELISA-measured IgG PNC antibody concentrations at week 4 in Step 1, in the women who received PPV-23 or PCV-10, and the following variables (measured at week 0):
    - maternal age,
    - ethnicity,

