## 5.4 Secondary Objectives

Summaries will include:

- i) means (or medians if data are not normally distributed) and 95% CI of mean ratio of infant/mother ELISA-measured IgG PNC antibody levels across the serotypes listed above, measured at birth/delivery;
- ii) Summary table with proportion (%) and 95% CI of women in the each treatment group who had a  $\geq$ two-fold increase to each serotypes in ELISA-measured IgG PNC antibody concentrations from baseline to week 4 after immunization in Step 1;
- iii) Summary table with proportion (%) and 95% CI of women by treatment arm who had ELISA-measured IgG PNC antibody levels  $\geq 0.35\text{ug/mL}$  at week 4 after immunization in Step 1, at labor&delivery, and at week 24 post-delivery in Step 1 to  $\geq 1$  of the serotypes listed above;
- iv) Summary table with proportion (%) and 95% CI of women who had a two-fold increase to  $\geq 1$  serotype in ELISA-measured IgG PNC antibody concentrations from baseline to week 4 after immunization in Step 1 vs the women who achieved this from entry to Step 2 until week 4 post immunization in Step 2 (for each of the two vaccines). The analyses will exclude the women who delivered prior to week 4 in Step 1;
- v) Correlations between ELISA-measured IgG PNC antibody concentrations at weeks 4 in Step 1, in the women who received PPV-23 or PCV-10, and the following variables (measured at week 0): maternal age, ethnicity, cluster of differentiation 4 (CD4) count, cluster of differentiation 8 (CD8) count, plasma HIV RNA and gestational age;
- vi) Summary table with proportion (%) and 95% CI of infants born to mothers who received PCV-10 or PPV-23 vaccines who had ELISA-measured IgG PNC antibody levels  $\geq 0.35\text{ug/mL}$  at 16 and 24 weeks of age for  $\geq 1$  serotypes listed above;
- vii) Summary table with mean (95% CI) number of serotypes with levels  $\geq 0.35\text{ug/mL}$  at weeks 16 and 24 of age in study infants.

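### Maternal primary objective 2 lists IgG level and fold change as its outcome, but Section 5.3 compares the vaccines only on an any-of-eight responder share, with no between-vaccine estimate of level or fold change

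*SAP*

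**What the plan says.** Primary objective 2 in SAP Section 3.2 is comparative: "To compare the immunogenicity of PCV-10 with PPV-23 vaccines in HIV-infected pregnant women on HAART". Its single outcome measure is "Raw values and fold change in ELISA-measured IgG PNC antibody concentrations from baseline to week 4 in Step 1", qualified as applying to at least one of eight named serotypes. No responder cut-off is attached. The infant outcome for primary objective 3, in the same list, does carry one (0.35 ug/mL).

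The maternal part of Section 5.3 sets out two summaries in women vaccinated with either product:

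- (i) the share with at least a two-fold rise to at least one serotype, with 95% CIs and the statement that "The difference in proportions between the vaccinated groups will be assessed using a Chi-Square test";
- (ii) the share at or above 0.35 ug/mL at week 4 for at least one serotype, with 95% CIs and no named test.

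Section 5 adds a general rule for summarising "continuous data using N, min, Q1, median, Q3, max, and mean (STD) (when appropriate) and 95% CI". Section 5.4(ii) adds a "Summary table with proportion (%) and 95% CI of women in the each treatment group who had a" two-fold rise, serotype by serotype. Section 1 says the SAP covers "summaries of the primary and secondary outcome measures that will be posted on ClinicalTrials.gov" and leaves to a separate implementation plan the "Detailed outlines of tables and coding descriptions that will be included in the primary statistical analysis report".

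**The concern.** The listed outcome is a level and a change in level, and the objective is to compare two vaccines on it. The comparison actually specified uses a yes/no reduction of that outcome, pooled over eight serotypes by an any-of-eight rule. A woman who responds to one serotype counts the same as a woman who responds to all eight. If response per serotype is moderate or high, nearly every woman in both arms is a responder, and the test has little room to show a difference in antibody level.

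At stake is how well objective 2 is answered. The report could show per-arm medians, means and proportions side by side, yet give no estimate with an interval of how much more antibody one vaccine produces than the other.

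**Working it through.** **Step 1: the text.**

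| Place in SAP | Quantity | Between-vaccine contrast |
|---|---|---|
| 3.2, objective 2 | raw values, fold change | required by the objective |
| 5, continuous data | per-arm descriptive statistics, 95% CI | none |
| 5, general Chi-square sentence | response rates | vaccinated groups vs placebo |
| 5.3(i) | two-fold rise, at least 1 of 8 | Chi-square |
| 5.3(ii) | 0.35 ug/mL or above, at least 1 of 8 | none named |
| 5.4(ii) | two-fold rise, each serotype | none |
| 5.4(v) | correlation of week 4 level with covariates | none |

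No row gives a between-vaccine estimate or test of concentration or fold change on its own scale.

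**Step 2: inputs.** From the SAP: eight serotypes (3.2); at least 100 evaluable pairs per arm (3.1); two-sided 0.05 without multiplicity adjustment (5). The SAP states no power, effect size, response rate, SD or correlation, so there is no power figure to reproduce; the counts agree (2 × 345 = 690; 2 × 300 = 600; 300/3 = 100). Assumed for illustration: normal log fold rises with equal SD in both arms, common inter-serotype correlation ρ of 0.3, 0.5 or 0.7, and three pairs of per-serotype two-fold rates.

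**Step 3: ceiling.** With independent serotypes, P(any) = 1 − (1 − p)^8. For p = 20, 30, 40, 50% this is 83.2, 94.2, 98.3, 99.6%. With correlation, P(any) = 1 − ∫ Φ((c − √ρ z)/√(1 − ρ))^8 φ(z) dz, where c = Φ⁻¹(1 − p). Rates of 63 vs 75% then become 98.2 vs 99.5% (ρ = 0.3), 94.9 vs 98.0% (0.5) and 89.2 vs 94.7% (0.7).

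**Step 4: power at 100 per arm.** Chi-square power is exact (Pearson, no continuity correction, summed over all 2×2 tables). The comparator is a t-test on the mean log fold rise across the eight serotypes. Example, 63 vs 75%, ρ = 0.5: shift = Φ⁻¹(0.75) − Φ⁻¹(0.63) = 0.343 SD; SD of the mean = √((1 + 7 × 0.5)/8) = 0.75; 0.343/0.75 = 0.457; non-centrality 0.457 × √50 = 3.23; power 90%.

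| Shift | Per-serotype rates | Chi-square, any of 8 (ρ 0.3/0.5/0.7) | Mean log (ρ 0.3/0.5/0.7) |
|---|---|---|---|
| all eight | 63 vs 75% | 7/20/31% | 97/90/80% |
| all eight | 40 vs 55% | 47/54/56% | 99/95/87% |
| all eight | 20 vs 35% | 89/85/82% | >99/99/96% |
| four of eight | 63 vs 75% | 5/10/15% | 49/36/29% |
| four of eight | 40 vs 55% | 21/24/27% | 57/43/34% |
| four of eight | 20 vs 35% | 49/47/48% | 73/57/46% |
| four up, four down | 63 vs 75% | 4/6/10% | 5% |
| four up, four down | 40 vs 55% | 9/12/17% | 5% |
| four up, four down | 20 vs 35% | 22/27/36% | 5% |

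Much of the gap in the first three rows comes from averaging eight equal shifts. Dichotomising alone, for one serotype, takes power from 67, 76 and 90% (t-test) to 46, 59 and 67% (Chi-square) for the three pairs. Where serotypes move in opposite directions, the mean log cancels, but each shifted serotype compared separately keeps 67, 76 or 90%.

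**Step 5: what the planned tables show.** The half-width of a per-arm 95% CI is 1.96 √(p(1 − p)/100): 7.8 points at 20% and 9.8 at 55%, so about 8 to 10 points for each proportion in 5.4(ii).

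**Step 6: price of adding eight ratios.** With no true difference, the chance that at least one of eight unadjusted 95% CIs excludes 1 is 1 − P(all eight |z| < 1.96) = 30, 25 and 19% for ρ = 0.3, 0.5 and 0.7 (1 − 0.95^8 = 34% if independent).

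**The case against.** The case for leaving the plan as it stands has four parts.

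- **A prespecified responder share with a named test does answer a comparative objective.** This stands. Using responders is a legitimate choice, and Section 5.3(i) is plainly the only maternal test. A reader might infer that the Chi-square test is wrong and should be replaced; nothing in the SAP supports that.
- **The missing cut-off is not a gap in the analysis.** This also stands. Section 5.3 supplies both cut-offs. Section 3.2 is part of the protocol overview, so its silence is editorial.
- **Readers will have level data.** Correct. It is tempting to say that only separate per-arm proportions would be available. But Section 5 says continuous data will be summarised, and raw values and fold change are continuous. What is missing is the contrast between vaccines, with its interval.
- **The power loss rests on assumed inputs.** Correct. It can vanish or reverse: with four of eight serotypes shifted, 20 vs 35% and ρ = 0.7, the Chi-square test has 48% against 46% for the mean log, and with opposing shifts it exceeds the mean log in eight of nine cells. With independent serotypes at 20 vs 30%, the any-of-eight share (70%) also has more power than a single-serotype comparison of proportions (37%). One cannot say from the SAP that the test will miss a difference.

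The implementation plan is not at hand and might include such a table. The SAP describes it as holding table outlines and coding, while the SAP itself is meant to record the agreed analyses for the primary objectives. The finding therefore concerns the SAP only.

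**Conclusion.** The point holds in a limited form. The outcome listed for a comparative primary objective is level and fold change, and the SAP specifies no between-vaccine estimate of either. The one comparison uses an any-of-eight dichotomy that ignores how many serotypes respond and by how much.

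That textual gap holds whatever the response rates. The size of its consequence does not: it is severe if per-serotype response is moderate to high and all serotypes shift together, and small or absent relative to a mean across serotypes if response is low or only some serotypes shift. The SAP gives no figure that would settle which applies. This is a worthwhile, inexpensive improvement to the plan, not an error that invalidates the primary test.

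**What to change.** Keep the Chi-square test in Section 5.3(i) as the primary test for objective 2, with 5.3(ii) descriptive. Add to Section 5.3, labelled as supporting:

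- a linear model of log week 4 concentration on arm (PCV-10 vs PPV-23) and log baseline concentration, in women vaccinated with either product;
- the geometric mean ratio with 95% CI for each of the eight serotypes;
- secondarily, the same ratio for the mean log across the eight, with a note that opposing serotype effects can cancel in it.

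One model serves both level and fold change. Log fold change is log week 4 minus log baseline, and with log baseline in the model the arm coefficient is the same for either response. Precision is no worse than the fold-rise figures above: with baseline to week 4 correlation r and equal SDs, the variance is (1 + r)/2 of that of the fold rise. For 63 vs 75% in all eight serotypes and ρ = 0.7, mean-log power becomes 94, 90 or 84% for r = 0.3, 0.5 or 0.8, against 80%.

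As an editorial correction, write the two-fold and 0.35 ug/mL definitions from Section 5.3 into Section 3.2.

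The cost is SAP wording and one table from data already collected, plus nine unadjusted estimates. The 19 to 30% chance of a false lead among the eight ratios is why they should be stated not to replace the primary test. Section 5.1 describes visits in the past tense, so timing matters: date the change before the team has seen post-entry antibody data and before unblinding. Otherwise label it post hoc, in line with Section 5: "Any modifications to outcome measures after the team has seen data collected after entry will be identified as" such.
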